## A. Primary Endpoint

The operational definition of attainment of adult height was defined as the study visit at which the incremental growth declined <1.5 cm (0.6 inch) over 12 months.

The primary outcome variable is adult height which will be expressed in SD units relative to the normal population.

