# **B** Secondary Endpoints

Secondary outcome variables will be examined between the two study arms at baseline, pubertal onset and adult height (final visit). To examine sex differences, the secondary outcomes variables will be examined by-sex between the two study arms.

'Pubertal Onset' is defined as the visit when patients entered puberty (Tanner 2 breast in females, testicle size > 3mL) or completed therapy with the aromatase inhibitor and or LHRHa.

- i. Adult height achieved will also be expressed standard deviation (SD) units and in cm as the difference in height achieved in relation to their target height (i.e., mid-parental height, calculated based on their parental heights)
- ii. Height achieved (SD units) from baseline to pubertal onset
- iii. Height achieved (SD units) from pubertal onset to adult height
- iv. Predicted adult height (using Bayley-Pinneau method) at pubertal onset
- v. Predicted adult height (using Bayley-Pinneau method) change from baseline to pubertal onset
- vi. Predicted adult height (using Bayley-Pinneau method) change from pubertal onset to final height
- vii. Growth velocity (in SD units) from baseline to pubertal onset
- viii. Growth velocity (in SD units) from pubertal onset to adult height
- ix. Percent of visits with ACTH in normal range from baseline to pubertal onset
- x. Percent of visits with ACTH in normal range from pubertal onset to adult height
- xi. Percent of visits with androstenedione in normal range from baseline to pubertal onset
- xii. Percent of visits with androstenedione in normal range from pubertal onset to adult height
- xiii. Percent of visits with 17-hydroxyprogesterone in the optimal range (<1,200 ng/dL) or high (>1,200 ng/dL) from baseline to pubertal onset
- xiv. Percent of visits with 17-hydroxyprogesterone in the in the optimal range (<1,200 ng/dL) or high (>1,200 ng/dL) from pubertal onset to adult height
- xv. Percent of patients with onset of central precocious puberty (CPP)

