Choice of medication will be based on patient and family preferences. Families will be counseled on the advantages and disadvantages of these two therapies. Both medications are known to effectively suppress the hypothalamic-pituitary-gonadal axis. Known side effects include rash, and local injection site reactions (milder with Deslorelin). Lupron has the advantage of monthly administration and the disadvantage of an increase risk of local injection site abscess formation (Deslorelin may cause redness at the injection site but has not been reported to result in abscess formation). Lupron also may require more dose adjustments in the beginning of therapy. Anaphylactoid reactions are an extremely rare risk for both medications. Children will return to the NIH day hospital 3 months after starting LHRH analog therapy for evaluation of hypothalamic-pituitary-gonadal suppression. Those patients who are currently being treated with Deslorelin (previously under protocol 79-CH-112) will be continued on Deslorelin or switched to Lupron, depending on patient preference.

Once degree of CAH control has been judged optimal, children will be randomized to receive either the regimen of flutamide, testolactone or letrozole, and reduced hydrocortisone dose or conventional treatment (with hydrocortisone and fludrocortisone) until the age of 13 in the girls and 14 in the boys. At that time the regimen of flutamide, testolactone, and reduced hydrocortisone dose will be discontinued in boys so that the subjects can progress through puberty. At age 13 years, girls who are receiving flutamide and testolactone or letrozole therapy will discontinue the aromatase inhibitor therapy (to allow normal progression of puberty) and continue flutamide (to continue androgen blockade). Flutamide therapy will continue until 2 years after menarche or when final height is reached, whichever occurs first.

Children who are also receiving concurrent LHRH analog to suppress central puberty will also discontinue this agent at age 13 in the girls or age 14 in the boys. The operational definition of age 13 or 14 will be the NIH study visit that is closest to their thirteenth or fourteenth birthday. The operational definition of attainment of final height, as in our other long-term trials, will be the study visit at which the incremental growth over the previous 12 months declines to less than 1.5 cm (0.6 inch).

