#### Analysis of Study (please also see attached SAP Appendix A)

- The primary outcome (adult height expressed in SD units) will be compared between groups at the conclusion of the study using the unpaired two-tailed Student's t-test, or nonparametric Wilcoxon rank sum test, as appropriate
- Secondary outcome measures during the study include hormone levels (percent of visits in ranged defined above) and treatment doses, BMI (as SD units), final BMD (Z-score), growth velocity (in SD units), rate of bone maturation, and predicted adult height (Bayley-Pinneau method, automated software in a subset of patients) at baseline, pubertal onset, and final visit. These outcomes will be compared between the study arms by multivariable mixed models for repeated measures. These models will allow for within-subject comparisons between timepoints, as well as account for their correlations across time, adjust for potential confounders, and specify the appropriate outcome distribution (e.g., normal, binomial, or Poisson distribution for type of data). They are a robust method for accommodating missing data, especially in measures that are repeated and collected longitudinally. Post-hoc comparisons will identify the driving factors and group effect influencing any observed differences, and will be corrected for multiple comparisons as applicable.

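### Read literally, the plan compares growth velocity SD score at a visit defined by near-zero growth, where the score mainly reflects the age at which growth stopped

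*Combined protocol and SAP*

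**What the plan says.** Under Analysis of Study, the secondary outcomes include "growth velocity (in SD units), rate of bone maturation, and predicted adult height", listed "at baseline, pubertal onset, and final visit. These outcomes will be compared between the study arms by multivariable mixed models for repeated measures". The lead-in to section B, Secondary Endpoints, uses the same three time points and equates the last one with adult height: "Secondary outcome variables will be examined between the two study arms at baseline, pubertal onset and adult height (final visit").

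Section A, Primary Endpoint, defines the adult-height visit as "the study visit at which the incremental growth declined <1.5 cm (0.6 inch) over 12 months". The Protocol section gives the same rule explicitly as a look-back: "the study visit at which the incremental growth over the previous 12 months declines to less than 1.5 cm (0.6 inch").

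The numbered endpoints in section B are worded differently. Item vii is "Growth velocity (in SD units) from baseline to pubertal onset" and item viii is "Growth velocity (in SD units) from pubertal onset to adult height". Both are velocities over an interval, not at a visit.

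Secondary Objectives names growth velocity only for the period before puberty. For puberty itself it names height gain and bone maturation.

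The text does not say which form of velocity enters the mixed model, over what window it is measured, which reference gives the SD score, or whether age is a covariate. Analysis of Study refers to SAP Appendix A, which is not in the text available for this review.

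**The concern.** The final visit is selected on the value of the outcome that is then compared there. Whatever a child's treatment, growth over the 12 months before that visit is under 1.5 cm, because otherwise it would not be the final visit. Converting that small number to an SD score for age brings in the growth of peers. A child who stops early is compared with peers who are still growing and scores very low. A child who stops late is compared with peers who have nearly stopped and scores near zero.

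This matters because the trial hypothesises a change in the timing of maturation. The Introduction includes the aromatase inhibitor to block estrogen's maturing effect on bone. The first criterion under Evaluation of the Project cites late growth-plate closure in people who lack estrogen action. If the regimen works that way, treated children should stop growing later and score less negatively at the final visit for that reason alone. A reader of the results table would take this as a difference in growth rate.

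Endpoint viii has a milder form of the problem. Its interval closes at the same outcome-defined visit, so its denominator is the time growth took to finish, which treatment may change.

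**Working it through.** **Plan's own figure.** There is none to reproduce. The sample-size figures under Analysis of Study concern adult height, and no SD, effect or power is given for growth velocity.

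**Step 1: what the documents fix.** Final visit = adult-height visit (section B lead-in). Adult-height visit = growth under 1.5 cm in the previous 12 months (section A; Protocol section). So a 12-month velocity v at the final visit satisfies v < 1.5 cm in both arms, with no outside assumption.

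**Step 2: the SD score.** Score = (v − m) / s, where m and s are the reference mean and SD of velocity at the child's age. The documents give neither, so everything from here rests on assumed references.

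*At a fixed age*, the permitted range of v (0 to 1.5 cm) spans 1.5 / s. For s from 1.3 down to 0.5 cm/year this is 1.5/1.3 = 1.2 to 1.5/0.5 = 3.0 SD. Residual velocity therefore contributes something.

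*Across ages*, take one assumed curve for boys: after a peak of 9.5 cm/year at 13.5 years, m = 9.5 × exp(−((age − 13.5)/1.9)²), with s = 0.8 cm/year at these ages. Hold v at 0.75 cm, the middle of the range:

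| Age at final visit | m (cm/year) | Score = (0.75 − m)/0.8 |
|---|---|---|
| 16.0 | 1.68 | −1.17 |
| 16.5 | 0.79 | −0.04 |
| 17.0 | 0.32 | +0.54 |

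Identical growth scores 0.54 − (−1.17) = 1.71 SD higher when it is observed one year later.

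**Step 3: simulation over a range of assumptions.** Inputs, all assumed except the cap on v:
- v uniform on 0–1.5 cm;
- reference peak 9.5 cm/year at 13.5 years (boys) or 8.3 cm/year at 11.5 years (girls);
- reference SD 1.0–1.3 cm/year at the peak, with a floor of 0.5–1.0;
- mean stopping age 2.5 years after the peak, with SD 0.5–1.0 year;
- 23 per arm, from 30 × 0.75 = 22.5 after the plan's 25% drop-out.

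| Arm shift in stopping age | Difference in final-visit score | Chance of p < 0.05 |
|---|---|---|
| 0 | 0 | 5% |
| 0.5 year | 0.8–1.8 SD | 31–81% |
| 1 year | 1.3–2.9 SD | 78–100% |

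With no shift, stopping age explains about 85–97% of the variance of the score.

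**Step 4: endpoint viii.** Suppose one child gains 20 cm in 3 years and another 25 cm in 5 years. In raw units the second is slower: 20/3 = 6.7 against 25/5 = 5.0 cm/year. Endpoint viii is in SD units, however. Assume both start at the same age, with peers at 6 (SD 1.2) cm/year for three years and 1 (SD 0.8) for the next two:
- first child: (6.67 − 6)/1.2 = +0.56;
- second child: reference mean (3×6 + 2×1)/5 = 4.0 and SD (3×1.2 + 2×0.8)/5 = 1.04, so (5.0 − 4.0)/1.04 = +0.96.

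The order reverses. Endpoint viii depends on how long growth lasted, and the direction in SD units depends on the reference.

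**The case against.** The strongest reply is that no numbered endpoint is a velocity at the final visit. Items vii and viii define growth velocity over intervals. The sentence in Analysis of Study compresses many outcomes, and its three time points cannot apply literally to all of them: percentages of visits in range and rate of bone maturation are interval measures too. The time points may mark interval boundaries or attach only to predicted adult height, and SAP Appendix A may settle this. The ambiguity is genuine, and it is why the point is put as a literal reading. It does not dispose of the point, because the section B lead-in repeats the same time points for secondary outcomes generally, and the interval reading of viii still ends at the outcome-defined visit.

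Adjusting for confounders, which the plan allows in general terms, is not an answer. Age is not named, and age at stopping may itself be a consequence of treatment.

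Four stronger readings are tempting, and the documents do not support them:
- *The score measures only age at stopping.* Residual velocity and the reference SD also contribute (step 2).
- *The comparison will show a spurious arm difference.* The documents give no stopping ages by arm. With equal ages the expected difference is zero; with unequal ages it is a real consequence of randomised treatment under the wrong name.
- *Endpoint viii will count against a regimen that works.* That follows in cm/year but not necessarily in SD units (step 4).
- *The pubertal objective would be answered wrongly.* That objective concerns height gain and bone maturation, which endpoints iii and xvi address directly.

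**Conclusion.** The concern holds in limited form. That velocity at the final visit is capped in both arms follows from the plan's own definitions. That its SD score mainly reflects age at stopping, and the sizes given, rest on assumed reference curves and stopping ages. On those assumptions a half-year arm shift would often, and a one-year shift usually, produce a statistically significant difference that says little about growth rate. Whether any shift occurs is unknown from the documents, although the regimen's rationale makes one plausible.

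Endpoint vii is sound. Endpoint viii is interpretable only beside the length of its interval. The matter is confined to secondary outcomes, and the primary comparison of adult height is untouched. A wording change before analysis is still worthwhile, because no stated objective needs growth velocity at the final visit.

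**What to change.** 1. In Analysis of Study, remove the final visit as a time point for growth velocity, so that the text agrees with endpoints vii and viii. Make the section B lead-in consistent.
2. Keep endpoint vii as the growth-velocity measure for the pre-pubertal interval.
3. Interpret endpoint viii only alongside height gained from pubertal onset to adult height (endpoint iii, reported in cm as well as SD units) and the years taken.
4. Report age at attainment of adult height as an outcome in its own right, so that any effect on timing appears under its proper name.
5. State the measurement window and the reference standard for the velocity SD score.
6. Align SAP Appendix A with these changes.

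The cost is wording. Heights are already measured at the 6-monthly visits, so nothing new is collected. The only loss is one uninformative secondary time point.

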Despite decades of study, the growth and development of most children with CAH remain abnormal [1, 2]. High levels of sex steroids induce premature epiphyseal closure; while excess glucocorticoid suppresses growth. The median adult height of treated boys was only at the 4th percentile of normal men, and the median adult height of girls, treated from before one year of age, was at the 25th percentile. Maria New and her colleagues reported adult height in all subjects that averaged 1.7 standard deviations below the mean for the normal population, which corresponds to the 9th percentile [3]. These are the results at leading clinics which pioneered hydrocortisone treatment of CAH. Moreover, retrospective studies indicate that the final height of treated patients is relatively independent of the degree of control of adrenal androgen levels, [1, 3-5] suggesting that both hyperandrogenism and hypercortisolism contributed to the observed adult short stature. A meta-analysis of data from 18 centers showed that adult heights in patients with classic CAH averaged 1.4 SD (10 cm) below the population mean [6]. A subsequent meta-analysis of 35 studies of classic CAH found the mean adult height score corrected for parental height of -1.05 standard deviation and mineralocorticoid use was associated with improved height outcome [7]. In addition, many girls encounter problems related to excess androgen despite treatment. Thus, there is need for continuing research to improve the outcome of treatment.

The suboptimal outcome of treatment is related to the theoretical inadequacy of fludrocortisone and hydrocortisone as sole treatment. If hydrocortisone is administered so as to

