We have chosen a group size of 30, giving this study the same statistical power as the study of Deslorelin-induced pubertal delay (83-CH-199). With an expected standard deviation of 6 cm for the final height measurements (approximately that of the normal population), the group size required to give a 80% power to detect a 5-cm difference (about 2 inches) at a p<0.05 is 24. The group size needed to detect a 6-cm difference is 17. This is regarded by the pediatric endocrine community as a reasonable power for a growth study - for example, the Genentech Collaborative Study of Turner Syndrome had a group size of 17. Thus, the study is designed to detect at least a 5 cm difference in final height, a clinically meaningful difference, and allows for a 25% drop out rate over the course of the study. This is regarded by the pediatric endocrine community as a reasonable power for example, the Genentech Collaborative Study of Turner Syndrome had a group size of 17. Thus, the study is designed to detect at least a 5 cm difference in final height, a clinically meaningful difference, and allows for a 25% drop out rate over the course of the study - for example, the Genentech Collaborative Study of Turner Syndrome had a group size of 17. Thus, the study is designed to detect at least a 5 cm difference in final height, a clinically end by the pediatric endocrine community as a reasonable power for a growth study - for example, the Genentech Collaborative Study of Turner Syndrome had a group size of 17. Thus, the study is designed to detect at least a 5 cm difference in final height, a clinically meaningful difference, and allows for a 25% drop out rate over the Degree **19** of **26** 

Abbreviated Title: Congenital Adrenal Hyperplasia Version Date: 03/23/2023

course of the study.

Please find attached study analysis plan.

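### The sample size rests on a 6 cm SD taken as roughly the normal-population value, but the Introduction's conversion implies about 7.1 cm, at which 24 per group gives about 66% power for 5 cm.

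*Combined protocol and SAP*

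**What the plan says.** The sample-size paragraph under Analysis of Study works in centimetres. Its variability input is given as: "With an expected standard deviation of 6 cm for the final height measurements (approximately that of the normal population". No other support for 6 cm is offered. Two results follow: "the group size required to give a 80% power to detect a 5-cm difference (about 2 inches) at a p<0.05 is 24", and "The group size needed to detect a 6-cm difference is 17". The planned size is larger: "We have chosen a group size of 30".

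The endpoint is on a different scale. Under A. Primary Endpoint: "The primary outcome variable is adult height which will be expressed in SD units relative to the normal population". The planned comparison is the "unpaired two-tailed Student's t-test, or nonparametric Wilcoxon rank sum test, as appropriate".

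The Introduction, summarising a meta-analysis, gives a conversion between the two scales: "adult heights in patients with classic CAH averaged 1.4 SD (10 cm) below the population mean".

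**The concern.** Two sections put a number on the spread of height in the normal population, and the numbers differ: 6 cm in the sample-size paragraph and about 7.1 cm by implication in the Introduction. The second is 19% larger (7.14/6 = 1.19).

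The stated power leaves almost no room for this. With 24 per group, 80% power for 5 cm requires a within-arm SD of about 6.05 cm or less. No sensitivity to a larger SD is given, and the effect is never expressed in the SD units in which it will be tested.

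At stake is how a null result would be read. The protocol calls 5 cm clinically meaningful and says the study is designed to detect it. If the within-arm SD is nearer 7.1 cm, a true 5 cm benefit would be missed about one time in three with 24 per group, against the one in five that the stated power implies.

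**Working it through.** **Inputs.** From Analysis of Study: SD 6 cm; differences of 5 and 6 cm; 80% power; two-sided 0.05; unpaired t-test; 24, 17 and 30 per group. From the Introduction: 1.4 SD = 10 cm.

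**Method.** Two-sample t-test with n per group, standardised difference d = difference/SD, 2n − 2 degrees of freedom, noncentrality d × √(n/2), power from the noncentral t distribution.

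**Step 1. Reproduce the plan.**
- 5 cm: d = 5/6 = 0.833. With n = 24 the noncentrality is 0.833 × √12 = 2.89 and power is 80.7%. The smallest n reaching 80% is 24.
- 6 cm: d = 6/6 = 1. With n = 17 power is 80.7%. The smallest n is 17.

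Both figures match exactly. One-sided versions give 19 and 14, so the plan used the two-sided t-test.

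**Step 2. SD implied by the Introduction.** 10/1.4 = 7.14 cm per population SD. If both figures are rounded, the range is 9.5/1.45 = 6.55 to 10.5/1.35 = 7.78 cm. Six lies outside it.

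**Step 3. Power for 5 cm if the within-arm SD equals one population SD** (1.0 on the primary scale).

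| cm per SD | d for 5 cm | Power, 24 per group | Power, 30 per group | n per group for 80% |
|---|---|---|---|---|
| 6.00 (plan) | 0.83 | 80.7% | 88.8% | 24 |
| 6.55 | 0.76 | 73.5% | 82.8% | 28 |
| 7.14 | 0.70 | 66.1% | 76.0% | 34 |
| 7.78 | 0.64 | 58.7% | 68.7% | 39 |

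The normal approximation gives much the same at 7.14 cm: 67.9% with 24, 77.4% with 30, and 33 per group for 80%.

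**Step 4. The 6 cm claim at 7.14 cm per SD.** d = 6/7.14 = 0.84. Power with 17 per group is 66.1%, and 80% needs 24 per group.

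**Step 5. Detectable difference.** With 24 per group and 80% power, d = 0.826, which at 7.14 cm per SD is 0.826 × 7.14 = 5.9 cm.

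**Step 6. Does the change of scale matter in itself?** If the within-arm SD really is 6 cm while one reference SD is 7.14 cm, the within-arm SD is 6/7.14 = 0.84 SD units and 5 cm is 0.70 SD units. The ratio is 0.70/0.84 = 0.833, so power is again 80.7%. What moves power is the within-arm SD, not the unit.

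**The case against.** The strongest reply is that power depends on the spread among trial patients, and the plan states an expectation for exactly that: 6 cm. The normal population enters only as a parenthetical comparison, and only approximately. Height in SD units has an SD of 1 in the reference population by construction, but not necessarily in treated patients with this disorder. No section gives an observed within-arm SD. This stands, and it is why the 66% must be stated conditionally.

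It is also fair that 7.14 cm is back-calculated from a background sentence about a source that cannot be checked here. The Introduction's conversions are loose elsewhere: it equates 1.7 SD below the mean with the 9th percentile, whereas a normal distribution gives about the 4.5th. So the documents do not show which of the two sections is wrong. The attached SAP (Appendix A) was not in the text available for this point, so whether it restates the power basis could not be checked.

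Three stronger readings are tempting and are not supported:
- A reader might infer that 24 and 17 are miscalculated. They are right for a 6 cm SD; the dispute is over the input.
- A reader might infer that testing in SD units by itself lowers power. Step 6 shows that it does not.
- A reader might infer that the shortfall persists even if all 30 per group complete. At 7.14 cm it does (76.0%), but at the lower rounding limit 30 per group reaches 82.8%.

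What the reply does not remove is the conflict. The plan's only stated support for 6 cm is its closeness to the normal-population value, and the Introduction's figure for that value is higher even after rounding. The plan makes no argument that treated patients vary less than the population.

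**Conclusion.** The point holds as an unreconciled input. On the plan's own premise that the arms vary about as the normal population does, and with the Introduction's conversion, power for 5 cm is about 66% with 24 per group and 76% with 30, and a 6 cm difference needs about 24 per group. With 24 per group, the number to which the 80% claim is attached, power stays below 80% over the whole rounding range.

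This rests on a common within-arm SD of 1.0 SD unit, the two-sided t-test at 0.05, and the Introduction's figures taken at face value. It should not be read as proof that the true SD is 7.1 cm or that true power is 66%. Nor is the primary analysis biased, since it uses the observed SD. What is affected is the stated power and how a null result would be interpreted. The dropout allowance is a separate matter and plays no part in these figures.

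**What to change.** Reconcile the SD in the sample-size paragraph with the Introduction's conversion, and restate power on the primary scale. Suggested wording:

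> Assuming a within-arm SD of 1.0 SD unit, 24 completers per arm give 80% power for a difference of 0.83 SD (about 5.9 cm at 7.1 cm per SD). Power for 5 cm (0.70 SD) is about 66% with 24 and 76% with 30 per arm.

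Keep the 24 and 17 per group figures only as conditional on a within-arm SD of about 0.84 SD units (6 cm at 7.1 cm per SD), with a stated justification for that value. If the sponsor instead holds that 6 cm is the right population SD, the Introduction's conversion needs explaining, and a sensitivity line for a larger SD should be added. Carry the same text into the SAP.

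The cost is wording in one paragraph and the SAP, and a less favourable stated power. Enrolment, endpoint and test are unchanged.

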#### Principal Investigator:

[name]

**Number and type of patients**: 62 patients with Congenital Adrenal Hyperplasia Accrual Ceiling: 62

	Number	Sex	Age Range
Patients	62	male and female	ages 2-18
Volunteers	0	V U	-

Multi-site study: No

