# Précis

To test the hypothesis that the regimen of flutamide (an antiandrogen), testolactone or letrozole (an inhibitor of androgen-to-estrogen conversion), and reduced hydrocortisone dose can normalize the growth and adult stature of children with congenital adrenal hyperplasia, and can avoid the complications of supraphysiologic glucocorticoid dosage, 60 children with this disorder will be randomized to receive either the above regimen or conventional treatment until they have reached age 13 years in a girl or age 14 in a boy. After these ages boys will receive conventional treatment and girls will receive conventional treatment plus flutamide. In girls, flutamide will be continued until 6 months after menarche. All children will be followed until they have attained final adult height. The principal outcome measures will be adult height, body mass index, and bone density.

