#### Monitoring and Criteria for Withdrawal of Subjects from Study

Patients will be monitored every 3 months, with visits alternating between their local physician and NIH (every 6 month visit to NIH). At the visit to the local physician, a single blood sample

will be obtained and sent to NIH for analysis of the same hormonal measures and blood chemistries that are performed during NIH visits (see protocol section above). The other monitoring during NIH visits has been described in detail above.

In addition to this monitoring, patients who are randomized to flutamide will receive intensive monitoring of liver function as a precaution against flutamide-associated liver toxicity (see Risks below). This monitoring will consist of a blood sample to determine liver function every 2 weeks for the initial 3 months, every month for the next 9 months, and every 3 months thereafter.

Patients who experience flutamide-associated liver toxicity (the estimated incidence is 1 in 273 patients), or who do not tolerate the flutamide and aromatase inhibitor regimen, will be withdrawn from this treatment arm and followed on conventional treatment so that their outcome will be available for an intention-to-treat analysis. We will also ask patients who elect to withdraw from the study to continue to make semiannual height measurements at home and to return to NIH for one final height and weight measurement once they attain the final height criteria.

Since CAH is a chronic disorder requiring lifelong treatment, and since the final height of all subjects is important for the performance of an intention-to-treat analysis, we do not foresee circumstances that would lead us to withdraw a subject from study. If an unrelated illness, such as chronic active hepatitis, were to preclude use of the investigational regimen, we would nonetheless wish to follow the subject on the conventional treatment.

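### Thirty children per group allows for 20% loss of final heights, not the stated 25%: 30 × 0.75 = 22.5, below the 24 per group the plan requires

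*Combined protocol and SAP*

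**What the plan says.** The protocol's Analysis of Study section gives the sample size reasoning.

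- Variability: "With an expected standard deviation of 6 cm for the final height measurements (approximately that of the normal population").
- Requirement: "the group size required to give a 80% power to detect a 5-cm difference (about 2 inches) at a p<0.05 is 24". For a 6 cm difference it gives 17 per group.
- Choice: "We have chosen a group size of 30".
- Allowance: the design "allows for a 25% drop out rate over the course of the study". In the text supplied this statement appears three times in garbled, repeated sentences, with the same figure each time.

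The same section says that the primary outcome will be "compared between groups at the conclusion of the study using the unpaired two-tailed" t-test, or a rank sum test where appropriate. The Précis states that "60 children with this disorder will be randomized to receive either the above regimen or conventional treatment", and the front page gives "62 patients with Congenital Adrenal Hyperplasia Accrual Ceiling: 62".

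On retention, Monitoring and Criteria for Withdrawal of Subjects from Study says that "the final height of all subjects is important for the performance of an intention-to-treat analysis". Children who stop the investigational regimen are to be followed on conventional treatment, and those who leave the study are asked to come back for one last height measurement.

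**The concern.** A dropout rate is a share of those enrolled. Taking 25% from 30 leaves fewer than the 24 that the same paragraph says are needed, so the three figures (24, 30 and 25%) cannot all stand. The likely origin is that the allowance was added to the evaluable number (24 × 1.25 = 30) when the evaluable number should have been divided by the fraction retained. The documents show no formula, so this is inference.

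What is at stake is a stated design property. Children are followed to adult height, over many years, in a rare disease with capped accrual, so retention is the main protection for power. Someone who took 25% as the tolerable loss would accept 15 missing final heights when the design covers 12.

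**Working it through.** **Inputs.** Difference 5 cm, SD 6 cm, power 80%, significance level 0.05, required size 24 per group, chosen size 30 per group and dropout 25% all come from Analysis of Study, as does the two-tailed unpaired t-test. The total of 60 comes from the Précis and the ceiling of 62 from the front page. Allocation is 1:1 (Evaluation of Benefits and Risks/Discomforts gives a 50% chance of each arm).

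**Step 1: reproduce the plan's own sizes.** Power is that of a two-sided two-sample t-test (noncentral t), with standardized difference d = difference / SD and equal groups of n.

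- 5 cm: d = 5/6 = 0.833. The solution is n = 23.60, rounded up to **24**. Power is 80.7% at 24 and 78.9% at 23.
- 6 cm: d = 6/6 = 1. The solution is n = 16.71, rounded up to **17**. Power is 80.7% at 17 and 78.1% at 16.

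Both stated sizes reproduce exactly, so the inputs to the dropout step are sound.

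**Step 2: apply 25% loss to the chosen size.**

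- Per group: 30 × 0.75 = 22.5, below 24.
- In total: 60 × 0.75 = 45, below 2 × 24 = 48. The shortfall is 3 children.
- At the ceiling: 62 × 0.75 = 46.5, still below 48.

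**Step 3: find the loss that the design can absorb.**

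- With 60 randomized: 1 − 48/60 = 20.0%, or 12 children.
- With 62 randomized: 1 − 48/62 = 22.6%, or 14 children.

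**Step 4: find the size that 25% would require.** n / (1 − loss) = 24 / 0.75 = 32 per group, or 64 in all. That is 4 above the planned 60 and 2 above the ceiling. The other form, 24 × 1.25 = 30, gives the chosen size exactly, but 6 lost out of 30 is 20%.

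**Step 5: consequence for power (5 cm, SD 6 cm, two-sided 0.05).**

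| Final heights available | Power |
|---|---|
| 30 + 30 (no loss) | 88.8% |
| 24 + 24 (20% loss from 60) | 80.7% |
| 22 + 23 (25% loss from 60) | 78.0% |
| 23.25 per group (25% loss from 62) | 79.4% |

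Between 24 + 24 and 22 + 23, power falls by 80.7 − 78.0 = 2.7 points. The difference detectable with 80% power rises from 4.96 to 5.13 cm.

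**The case against.** The strongest reply concedes the arithmetic and disputes its weight.

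- **Dropout need not mean a lost height.** The protocol does not define dropout, and its withdrawal section tries to recover final heights from children who stop treatment or leave. If 15 of 60 drop out and 3 return for measurement, with the remainder balanced between arms, 48 heights are available. This stands as a reason to expect fewer missing outcomes. It does not rescue the sentence, which sets 25% against an evaluable group size and does not invoke that recovery. If dropouts kept their heights, no allowance for them would be needed.
- **The gap is within rounding and choice of formula.** The normal approximation needs 22.6 per group, and 22.5 per group then has 79.8% power. Two inches is 5.08 cm, for which 22 + 23 gives 79.3% by the t-test. This stands as evidence that the effect is small. The plan nevertheless states 24 and plans a t-test. Even with the approximation's 23 per group, 30 would allow 1 − 23/30 = 23.3%, still below 25%.
- **The comparison with the ceiling is fragile.** With 23 per group, the inflated size is 31 per group, or 62, which equals the ceiling. Also, some enrolled children may not be randomized, so 62 randomized is a best case. Both remarks are fair. The figure of 64 rests on the plan's own 24, and the main conclusion does not depend on the ceiling.
- **No rule uses 25%.** That is true of the supplied text: no retention, replacement or stopping rule refers to it. The harm is therefore potential, which bears on priority and not on correctness.

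**Conclusion.** The concern holds. On the plan's own figures, 30 per group allows for 20% loss of final heights (22.6% if 62 are randomized), and 25% is wrong as written. The consequence is modest: about 78% power after 25% loss from 60, which is 2.7 points below the power at the required size, and a shift of 0.17 cm (5.13 − 4.96) in the detectable difference. This is an error in a stated design figure and does not make the trial underpowered.

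The conclusion assumes a 5 cm difference and 6 cm SD as the plan gives them, the planned two-sided t-test at 0.05, 1:1 allocation with losses about equal between arms, and dropout read as loss of the primary outcome. The protocol refers to an attached SAP (Appendix A) that is not in the supplied text, so whether the allowance is restated there could not be checked.

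**What to change.** Correct the statement wherever it appears in the sample size paragraph, and in the attached SAP if it is repeated there. Either replace 25% with 20%, or keep 25% and give the power that goes with it. Suggested wording:

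> Twenty-four evaluable children per group give 80% power to detect a 5 cm difference (SD 6 cm, two-sided alpha 0.05). Thirty per group therefore allows for 20% loss of final heights; at 25% loss (45 children) power is about 78%.

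Referring to loss of final heights also removes the ambiguity about dropout.

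The cost is the rewording of one statement. No extra children are needed, and the endpoint, test and follow-up stay as they are. The stated allowance, or the stated power, becomes slightly less favourable.
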